6.2. Primary Efficacy Endpoint and Analysis

6.2.1. Definition

The primary efficacy endpoint of this study is the mean change from baseline (run-in period) in the monthly average number of CH attacks during the 12-week period after administration of the first dose of the IMP.

CH attacks will be derived from the e-diary data as described in Section 6.1.1. The 12-week period is the period from administration of the first dose of the IMP to the EOT/early withdrawal visit. Missing data handling methods are provided in Section 6.1.4.1.

6.2.2. Primary Efficacy Analysis

The hypothesis testing for the primary analysis is:

$$H_o : \delta_1 = \delta_2 \quad \text{vs} \quad H_a : \delta_1 \neq \delta_2$$

where δ_1 and δ_2 are the estimates of mean change from baseline in the monthly average number of CH attacks for the fremanezumab treatment group and the placebo group, respectively. To control overall type I error rate, the comparison of each active treatment group (fremanezumab 900-mg iv loading dose group and fremanezumab 675-mg sc loading dose group) versus the placebo will be tested using Hochberg's step-up method as described in Section 7.

The primary endpoint will be analyzed using an ANCOVA method. The model will include baseline preventive medication use (yes or no), gender, region (US/Canada or other), and treatment as fixed effects; the baseline number of CH attacks as a covariate. The least square (LS) mean and SE for each treatment group, LS means and corresponding 95% confidence intervals for the treatment differences (fremanezumab - placebo), and associated p-values will be presented.

The analysis will be performed on the FAS and PP analysis sets.

Example SAS code for ANCOVA

```
PROC MIXED DATA=<name>;
  CLASS TRTP SEX REGION BPMU;
  MODEL CHG= BASE BPMU SEX REGION TRTP /S ;
  LSMEANS TRTP /DIFF=CONTROL(("Placebo")) CL ALPHA=0.05;
  ODS OUTPUT LSMEANS= <name> DIFFS= < name> ;
RUN;
```

Where TRTP denotes the planned treatment group; BPMU denotes the baseline preventive medication use (yes or no); CHG denotes the change from baseline; and BASE denotes the baseline number of CH attacks. In bold are the SAS key words.

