##### **9.5.4.1. Primary Efficacy Analysis**

The primary efficacy endpoint, the mean change from baseline (run-in period) in the monthly average number of CH attacks during the 12-week period after administration of the first dose of the IMP, will be analyzed using an analysis of covariance (ANCOVA). The model will include treatment, baseline number of CH attacks, baseline preventive medication use (yes or no), gender, and region (US or other).

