2.2. Randomization and Blinding

Patients will be randomly assigned with stratification based on gender, country, and baseline concomitant preventive medication use (yes or no) in a 1:1:1 ratio to 1 of 3 treatment groups.

- **fremanezumab 900-mg intravenous (iv) loading dose group:** fremanezumab at 900 mg administered via an approximately 1-hour iv infusion and 3 placebo subcutaneous (sc) injections at visit 2 (week 0) followed by fremanezumab at 225 mg administered as single sc injections (225 mg/1.5 mL) at visits 3 and 4 (weeks 4 and 8, respectively)
- **fremanezumab 675-mg sc loading dose group:** placebo administered via an approximately 1-hour iv infusion and fremanezumab at 675 mg administered as 3 sc injections (225 mg/1.5 mL) at visit 2 (week 0) followed by fremanezumab at 225 mg administered as single sc injections (225 mg/1.5 mL) at visits 3 and 4 (weeks 4 and 8, respectively)
- **placebo group:** placebo administered via an approximately 1-hour iv infusion and 3 placebo sc injections at visit 2 (week 0) followed by placebo administered as single sc injections at visits 3 and 4 (weeks 4 and 8, respectively)

The sponsor, investigators, study staff (except for staff involved in bioanalytical analyses and interim analyses [by a third-party, unblinded statistician]), and patients will be blinded to treatment assignment throughout the study.

Randomization will be performed using electronic interactive response technology (IRT), a third-party vendor. The randomization code will be generated by IRT following specifications from the Biostatistics Department. A Teva statistician will be responsible for reviewing the dummy randomization codes, and the final randomization code will be maintained by the third-party vendor in a secure location.

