4.3. Region of Pooled Countries

The study is planned to be conducted in approximately 12 countries. The countries will be pooled to 2 regions (US/Canada and other).

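### Randomisation is stratified by country but the primary model adjusts only for a two-level region: if country is prognostic, some precision is given up, though the planned power and type I error hold

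*SAP*

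**What the plan says.** SAP 2.2 gives the allocation scheme: "Patients will be randomly assigned with stratification based on gender, country, and baseline concomitant preventive medication use (yes or no"). The three arms are of equal planned size. Protocol 5.8 names the same three factors.

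On the number of countries, SAP 4.3 says: "The study is planned to be conducted in approximately 12 countries". It continues: "The countries will be pooled to 2 regions (US/Canada and other"). No reason for two regions is given.

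The primary ANCOVA in SAP 6.2.2 reads: "The model will include baseline preventive medication use (yes or no), gender, region (US/Canada or other), and treatment as fixed effects", with "the baseline number of CH attacks as a covariate". The example code agrees: "MODEL CHG= BASE BPMU SEX REGION TRTP /S". Two of the three stratification factors therefore enter as randomised, and the third enters only as a two-level grouping.

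The MMRM in SAP 6.2.3.2 has the same region term. The multiple-imputation analysis (6.2.3.1) and the medication-day and oxygen-day endpoints (6.3.3, 6.3.4) refer back to the ANCOVA. The second and third secondary endpoints (6.3.2) refer back to the MMRM. The sensitivity analyses in 6.2.3 address missing data only.

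Protocol 9.5.4.1 defines the grouping differently: "baseline preventive medication use (yes or no), gender, and region (US or other"). SAP Section 17 nevertheless lists no changes from the protocol.

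**The concern.** Stratifying on a factor that predicts outcome balances it across arms, so its variation largely drops out of the treatment contrast. If the model omits the factor, the same variation stays in the residual. The model then reports a standard error larger than the one the design delivers, confidence intervals are wider than they need be, and the test rejects less often than its nominal level under the null. Here the omitted part is country within region.

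What is at stake is precision on the primary endpoint and on the secondary endpoints that reuse its model. The mechanism does not bias the estimate. It operates only to the extent that country predicts the change in attacks after region, baseline attacks, gender and preventive use are accounted for.

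**Working it through.** **The plan's own figure.** Inputs from SAP 2.4: difference 4, SD 8, two-sided alpha 0.05, 86 evaluable per arm, 14% discontinuation.

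- n per arm = 2 × (1.960 + 1.282)² × 8² / 4² = 84.1, so 85 by the normal approximation.
- SE at 86 per arm = 8 × √(2/86) = 1.220. Power = Φ(4/1.220 − 1.960) = 0.906. The noncentral t gives 0.903 at 86 and 0.8999 at 85, so 86 is the exact t-test size.
- 258 / 0.86 = 300 randomised.

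The stated sample size reproduces. It uses SD 8 and credits no covariate with reducing variance.

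**Degrees of freedom.** With 258 patients the region model has 7 parameters (intercept, two treatment terms, baseline, gender, preventive use, region), leaving 251. With 12 countries in place of region it has 17, leaving 241. With no variance reduction, noncentral t power is 0.9043 on 251 and 0.9042 on 241.

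**Closed form, assuming perfect balance within country.** Let r be the share of residual variance due to country within region. The region model reports SE 1.220; the true SE is 8 × √(1 − r) × √(2/86). At r = 0.10:

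- True SE = 1.157, so the reported SE is 1.220/1.157 = 1.054 times the true one.
- Actual alpha = 2 × [1 − Φ(1.960 × 1.054)] = 0.039.
- Power with region = Φ((4 − 1.960 × 1.220)/1.157) = 0.918.
- Power with country = Φ(4/1.157 − 1.960) = 0.933.

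At r = 0.05 the SE ratio is 1.026 and alpha 0.044. At r = 0.20 they are 1.118 and 0.028.

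**Why a simulation is also needed.** Twelve countries by gender by preventive use is 12 × 2 × 2 = 48 strata, and 300/48 is about 6 patients per stratum over three arms. Incomplete blocks leave some imbalance, so perfect balance is optimistic.

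The simulation used 10,000 runs per block size with 258 patients and permuted blocks of 3 or 6 within the 48 strata. Total residual SD was held at 8. Both models were fitted to the same data for one active arm against placebo. Each cell shows blocks of 3 / blocks of 6.

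| r | SE overstated, region model | Actual alpha, region model | Power %, region model | Power %, country model | Points forgone |
|---|---|---|---|---|---|
| 0 | 0.3% / 0.0% | 4.8% / 5.0% | 90.21 / 90.19 | 89.98 / 89.88 | −0.23 / −0.31 |
| 5% | 2.5% / 1.9% | 4.5% / 4.8% | 90.82 / 90.54 | 91.35 / 91.28 | 0.53 / 0.74 |
| 10% | 4.8% / 3.8% | 3.9% / 4.3% | 91.29 / 90.93 | 92.61 / 92.49 | 1.32 / 1.56 |
| 20% | 10.0% / 8.1% | 3.1% / 3.4% | 92.15 / 91.75 | 95.14 / 95.15 | 2.99 / 3.40 |

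Monte Carlo standard errors are about 0.2 points for alpha, √(0.05 × 0.95/10,000), and 0.3 points for a single power figure, √(0.9 × 0.1/10,000).

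The closed form is best read as an upper limit for SE inflation and alpha deflation. The gap is clearest at r = 0.20, where it gives 11.8% and 2.8% against 8-10% and 3.1-3.4% in simulation.

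**The case against.** A reader might infer that the primary standard errors are too large and that power is lost, as a matter of fact. The documents do not support that. No between-country variance is given, and four terms that could absorb country differences are already in the model. At r = 0 there is no inflation and the country model is marginally worse.

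A reader might also infer that the trial is underpowered or that its error rate is compromised. Neither follows. The 90% rests on SD 8 with no credit for covariates, and the simulated power of the region model stays above 90% throughout. Its departure from 5% is in the conservative direction.

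The strongest objection is to the remedy. SAP 4.3 already pools countries by prespecification, and adjusting for country would itself need pooling where numbers are small, so the dispute is only over how coarse the pooling should be. Sparse countries are a real problem: under SAP 2.5.2 the full analysis would run even after a futility stop, and 150 patients over 12 countries is about 12 per country. This stands as a reason for a pooling rule. It does not justify going straight to two groups, since the full trial averages 300/12 = 25 patients per country.

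It is also fair that no variance or effect figure is available for the other endpoints that reuse these models, so the sizes above apply to the primary endpoint only. The inconsistent definition of region is a documentation point that adds nothing to the argument about standard errors. The SAP's introduction says that the SAP prevails and that differences will be explained in the study report.

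**Conclusion.** The mismatch between design and model is certain; its consequence is conditional. If country predicts change beyond the terms in the model, the analysis is mildly conservative and gives up available precision: under 2 points of power for a share up to 10%, and about 3 points at 20%. If it does not, nothing is lost. Planned power and type I error control hold over the whole range examined.

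The case for change is the asymmetry: 0.2-0.3 points at risk if country is irrelevant, against up to about 3 points recovered and a correctly calibrated interval if it is not.

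These sizes rest on assumptions that are not in the documents: r between 0 and 20%; blocks of 3 or 6; country shares of 28% and 6% for two US/Canada countries and 6.6% for each of ten others; 30% women; 55% on preventives; normal errors; and no drop-out after allocation. Each comparison is taken at two-sided 0.05, as in the plan's own power statement.

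Independently of any assumption, region has two definitions, and SAP Section 17 does not record the difference.

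**What to change.** In SAP 6.2.2 and 6.2.3.2, replace REGION by COUNTRY, as used at randomisation, in the model text and the SAS code. The multiple-imputation analysis and the endpoints that refer to those sections then follow.

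Add a rule, fixed before unblinding, for pooling countries with very few patients within their region, and state that it also applies if the trial stops at the interim. Keep region for the subgroup analysis in 6.2.4. If the sponsor prefers to retain the two-region model as primary, the minimum is a stated reason and a sensitivity analysis adjusted for country.

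Separately, settle one definition of region across protocol 9.5.4.1 and SAP 4.3 and 6.2.2, and list the change in SAP Section 17.

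The cost is SAP wording, one model term, a pooling rule and about 10 degrees of freedom. Sample size, data collection and trial conduct are unaffected.

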6.2.3. Sensitivity Analyses for the Primary Efficacy Endpoint

Sensitivity analyses will be conducted to explore the impact of missing data in the primary efficacy analysis.

6.2.3.1. Analysis with Multiple Imputation Method

An MI method will be utilized to impute the monthly missing data. Monthly analysis windows will be derived using the algorithm described in Section 6.1.3. The number of CH attacks within each monthly analysis window will be calculated and prorated to 28 days using formula [1A].

Data with the monthly average number of CH attacks will be processed using the following steps:

- For patients with partial e-diary data (ie, have <10 days of data) in a monthly window, the number of CH attacks in that monthly window will be reset to missing before the MI procedure.
- For patients in the active treatment groups who withdraw from the study early with reasons of adverse event or lack of efficacy, missing values will be imputed using data from the placebo-treated patients by assigning these patients to the placebo group for data imputation purpose.
- Run SAS PROC MI procedure to create 10 sets of data.
- Within each imputed data set, for patients with partial e-diary data in a monthly window (ie, <10 days of data), the number of CH attacks in the monthly window will be replaced by

$$\Sigma(\text{observed } CH \text{ attacks during a monthly window}) + (28 - X) * \frac{\text{imputed value}}{28}$$

Where X denotes the number of days with e-diary within a monthly window.

- The monthly average number of CH attacks **during the 12-week period** after the first dose of the IMP will be the average of the values from 3 monthly analysis windows.

Each set of imputed data will be analyzed using an ANCOVA method in a manner analogous to the primary endpoint as described in Section 6.2.2. The LS means and SEs from each analysis will be output to a SAS data set.

The SAS MIANALYZE procedure will be used to generate the final LS means and SE for the treatment groups and the treatment differences (fremanezumab - placebo) as well as p-values associated with treatment differences. The 95% confidence intervals for the treatment differences will also be constructed.

The analysis will be performed on the ITT analysis set.

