### **4.3. Withdrawal Criteria and Procedures**

Each patient is free to withdraw from the IMP and/or study at any time, without prejudice to their continued care. Patients must be withdrawn from the IMP and/or study if any of the following events occur:

1. Patient withdraws consent or requests discontinuation from the IMP and/or study for any reason.
2. Patient develops an illness that would interfere with his/her continued participation.
3. Patient is noncompliant with the study procedures and assessments or administration of IMPs in the opinion of the investigator.
4. Patient takes prohibited concomitant medications as defined.
5. A female patient has a confirmation of pregnancy during the study from a positive pregnancy test.
6. The sponsor requests withdrawal of the patient.
7. Patient experiences an adverse event or other medical condition which indicates to the investigator that continued participation is not in the best interest of the patient.
8. The investigator and/or sponsor may withdraw an individual patient from the study at any time for any reason (eg, lack of efficacy, protocol deviation as defined in Section 10, noncompliance, or adverse event). In addition, patients with positive eC-SSRS findings or abnormal hepatic laboratory values (eg, ALT, AST, ALP, GGT, bilirubin [total, direct, or indirect], or INR) may meet criteria for discontinuation from the IMP as summarized in [Appendix J](#).

In the event that a patient was incorrectly randomized and has already started taking the study drug, a risk/benefit evaluation should take place between the investigator and sponsor and a strong clinical justification must be provided if the patient is not withdrawn from study drug.

Patients should be treated with standard of care after withdrawal from or termination of the study as appropriate.

Investigators should attempt to obtain information on patients in the case of withdrawal or discontinuation. Results of any evaluations and observations, together with a narrative describing the reason(s) for withdrawal, must be recorded in the source documents. The case report form (CRF) must document the primary reason for withdrawal or discontinuation.

See [Appendix F](#) for information regarding how the study will define and address lost to follow-up patients to help limit the amount and impact of missing data.

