If a patient is withdrawn from the study for multiple reasons that include also adverse events, the termination page of the CRF should indicate that the withdrawal was related to an adverse event. An exception to this requirement will be the occurrence of an adverse event that in the opinion of the investigator is not severe enough to warrant discontinuation but that requires the use of a prohibited medication, thereby requiring discontinuation of the patient. In such a case, the reason for discontinuation would be “need to take a prohibited medication” and not the adverse event.

Should a patient decide to withdraw after administration of the IMP or should the investigator decide to withdraw the patient, all efforts will be made to complete and report all observations up to the time of withdrawal. A complete final evaluation at the time of the patient’s withdrawal should be made and an explanation given as to why the patient is withdrawing or being withdrawn from the study.

The reason for and date of withdrawal from the study must be recorded on the source documentation and transcribed to the CRF. If a patient withdraws consent, every attempt will be made to determine the reason.

All protocol-specified procedures/assessments should be performed at the early withdrawal visit (see [Appendix B](#)). Patients who withdraw from the study will not be replaced. Patients who withdraw early will be offered the opportunity to enter the long-term safety study (Study TV48125-CNS-30058) for the purpose of evaluation of ADAs and safety (adverse events and concomitant medications) approximately 7.5 months after administration of the last dose of IMP in this study. These patients will not receive any doses of fremanezumab after completing participation in the current study and should be treated with standard of care as appropriate. A patient should only be designated as lost to follow up if the site is unable to establish contact with the patient after 3 documented attempts via 2 different methods (phone, text, e-mail, certified letter, etc). In the case of patients lost to follow-up, attempts to contact the patient must be made and documented in the patient’s medical records and transcribed to the CRF.

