### **2. Concomitant Medications Allowed and Disallowed**

#### Steroids:

Screening/run-in period and throughout the study: Systemic steroids are not allowed to be used in the treatment of cluster cycles during the screening/run-in period and for the duration of the study.

The only allowed steroids are intra-articular injection or ocular, ear drops, intranasal, inhaled, and creams for topical use.

Screening/run-in period: Disallowed if patient used systemic steroids to treat the current CH cycle or for any other indication to treat the current CH cycle within  $\leq 7$  days of screening.

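### The placebo-based imputation in SAP 6.2.3.1 omits a withdrawal code that Protocol 4.3 creates, omits never-dosed active-arm patients, and does not fit its placebo model on placebo patients alone

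*SAP*

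**What the plan says.** SAP 6.2.3.1 describes a multiple-imputation (MI) sensitivity analysis of the primary endpoint on three monthly windows. Where a window has fewer than 10 diary days, "the number of CH attacks in that monthly window will be reset to missing before the MI procedure". Placebo-based imputation is then limited to active-arm patients who "withdraw from the study early with reasons of adverse event or lack of efficacy, missing values will be imputed using data" from placebo-treated patients. It is carried out "by assigning these patients to the placebo group for data imputation purpose". On the population, the section states: "The analysis will be performed on the ITT analysis set". The intent-to-treat (ITT) set is all randomised patients (SAP 3.1).

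Protocol 4.3 lists the events that require withdrawal from the drug and/or the study. Item 4 is "Patient takes prohibited concomitant medications as defined". The same section sets the coding. A withdrawal for several reasons that include an adverse event is recorded as related to an adverse event, with one exception. If the investigator judges the event not severe enough for discontinuation but it "requires the use of a prohibited medication, thereby requiring discontinuation of the patient", then "the reason for discontinuation would be “need to take a prohibited medication” and not the adverse event". Protocol Appendix H gives one example of a disallowed class: systemic steroids for cluster cycles, from screening until the trial ends.

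The other analyses of this endpoint contain no placebo-based element. The primary analysis prorates the available diary days (SAP 6.1.4.1), and the second sensitivity analysis is a mixed model for repeated measures (SAP 6.2.3.2).

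**The concern.** The SAP's rule depends on two reason codes, while the protocol tells sites to use a third code for a defined set of adverse-event-driven withdrawals. The SAP does not mention that code. Two patients who leave because of an adverse event can therefore be imputed under opposite assumptions, depending on whether the event itself or the medicine it needed ended participation.

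Never-dosed patients are a second omission. The full analysis set excludes them (SAP 3.3), so they enter the analysis of the primary endpoint only through this MI. The protocol foresees them: an eligibility deviation found before dosing means that study drug is not given (Protocol 4, Appendix C). They have no post-dose data and are unlikely to carry either listed code.

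Third, the section says the imputations use data from placebo-treated patients. Re-labelling active dropouts as placebo adds their own on-drug months to the data that fit the placebo model.

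At stake is how much weight a reader can place on the one analysis that tests a departure from missing-at-random.

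**Working it through.** **The rules side by side.**

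| Active-arm patient | Reason under Protocol 4.3 | Imputed under SAP 6.2.3.1 from |
|---|---|---|
| Leaves because of an adverse event, or several reasons including one | Adverse event | Placebo |
| Leaves for lack of efficacy | Lack of efficacy | Placebo |
| Adverse event not severe enough for discontinuation, prohibited medicine needed | Prohibited-medication code | Own active arm |
| Randomised, never dosed | Unlikely to be either listed code | Own active arm |

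The entry 'own active arm' is an inference, because the SAP does not print the PROC MI model. It is a firm one: re-labelling patients as placebo changes nothing unless the imputation depends on treatment arm.

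**The plan's own figures.** SAP 2.4 gives a difference of 4, SD 8, two-sided alpha 0.05, at least 90% power, 86 completers per arm and 14% discontinuation.
- n per arm = 2 × (1.960 + 1.282)² × (8/4)² = 84.1, so 85. With 86 per arm, power is 90.6% (90.3% with the noncentral t).
- 258 / (1 − 0.14) = 300.

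The design figures reproduce.

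**Size of the gap.** The documents do not give the share of each reason code, the amount of follow-up missing or the within-patient correlation. These are assumptions:
- q = share of the active arm in the omitted group: 2% to 5%
- m = months missing, out of 3: 1 or 2
- ρ = correlation between months: 0.5 or 0.8

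Change in the estimated difference if the group moves from own-arm to placebo-based imputation = 4 × q × (m/3) × (1 − k).

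Here k = 0 if benefit is taken to stop at once. If the patient's o observed months enter the model, k = oρ / (1 + (o − 1)ρ).

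| q | m | k | Change (attacks per month) |
|---|---|---|---|
| 2% | 1 | 0.667 (o = 2, ρ = 0.5) | 4 × 0.02 × 1/3 × 0.333 = 0.009 |
| 2% | 1 | 0 | 4 × 0.02 × 1/3 = 0.027 |
| 5% | 2 | 0.5 (o = 1, ρ = 0.5) | 4 × 0.05 × 2/3 × 0.5 = 0.067 |
| 5% | 2 | 0 | 4 × 0.05 × 2/3 = 0.133 |

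The range is therefore about 0.01 to 0.13 attacks per month. With ρ = 0.8 the low end falls to 0.003.

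**Outer limit.** If every dropout (14%) were imputed from placebo, with half of follow-up missing and immediate loss of benefit: 0.14 × 0.5 × 4 = 0.28. With two of three months missing it is 0.14 × 2/3 × 4 = 0.37.

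**Scale.** With 100 per arm the standard error is 8 × √(2/100) = 1.13. So 0.13 is 0.12 standard errors and 0.28 is 0.25 standard errors.

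**Make-up of the placebo model.** Suppose half of the 14% dropout among about 200 active patients carries a listed code: 200 × 0.14 × 0.5 = 14 patients are re-labelled beside about 100 placebo patients, or 14/114 = 12% of the group fitting the model. The half is an assumption, and patients contribute only the months they have.

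**The case against.** The case for leaving the rule alone is that reason-based imputation is explicit and prespecified, and no success claim in SAP 7 depends on it. Several stronger readings also fail, and the objection is right about each.

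- A reader might infer that every patient who leaves over a prohibited medicine is missed. The protocol's default runs the other way: a multi-reason withdrawal that includes an adverse event is coded as one. A patient given steroids for uncontrolled attacks could be coded lack of efficacy, which the rule covers. After randomisation, butalbital and opioids are allowed as needed (Appendix H), so the prohibited list is short. Nor do the documents treat steroid use as a sign of treatment failure; the rationale in Letter of Clarification 04 is that steroids can hide an improvement.
- A reader might infer that these patients are credited with the full drug effect. The text does not establish this. The PROC MI model is not printed, and if it includes earlier months, a poor course is partly carried forward. Windows with 10 or more diary days are not imputed at all. Mean half-life is 32.2 to 36.2 days (Protocol 1.2.2.1), so 55% to 59% of a given level remains after 28 days. Immediate loss of benefit is thus an upper-bound assumption.
- A reader might infer that a large part of the intended stress test is missing. The SAP never intended placebo-based imputation for every dropout, so that measures it against a different analysis.
- Treating consent withdrawal and loss to follow-up as missing at random is a modelling choice, not an error.
- Never-dosed patients should be few, because randomisation and first dose fall on the same day (SAP 4.5).
- The effect of re-labelling could go either way. On-drug months of lack-of-efficacy dropouts may be poor, which would make the placebo-based imputations more conservative.

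What remains is that the protocol's coding instruction and the SAP's rule do not fit together, never-dosed active-arm patients have no suitable rule, and the mechanics differ from the stated source of the imputations.

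**Conclusion.** The point holds as a mismatch between the two documents in one sensitivity analysis. Withdrawals given the prohibited-medication code, and never-dosed active-arm patients, fall outside the placebo-based rule, and no other planned analysis of the primary endpoint covers them that way. The placebo model is also not confined to placebo patients; the direction of that effect is unknown.

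The likely size is small: about 0.01 to 0.13 attacks per month for the prohibited-medication group, against an assumed effect of 4 and a standard error of about 1.13. This rests on assumed shares of 2% to 5% of the arm and one or two months missing. The 0.28 for all dropouts is only a yardstick. The gap could change the reading of the sensitivity analysis only for a borderline result, and it leaves the primary ANCOVA and the testing sequence untouched. It is worth correcting because the correction is cheap and the assumption should not depend on how a site codes the same kind of withdrawal.

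**What to change.** In SAP 6.2.3.1:

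1. Add the protocol's prohibited-medication withdrawal code, and active-arm ITT patients who were never dosed, to the placebo-based group. State the imputation rule for each remaining withdrawal reason on the case report form.
2. Fit the placebo imputation model only on patients randomised to placebo, for example with the MNAR statement of PROC MI and its MODELOBS option, in place of re-labelling active patients. Print the imputation model, including whether earlier months enter it.
3. Add, without replacing the reason-based version, an analysis that applies placebo-based imputation to all active-arm early withdrawals whatever the coded reason.

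The cost is SAP wording, a little more programming and a slightly less favourable sensitivity estimate. Sample size, data collection and the primary analysis do not change.
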